The primary aim of phase 2 (*feasibility/piloting*) is testing the feasibility of the planned implementation process.

Objectives are:

1. To evaluate the feasibility of eIPOS use in terms of participant recruitment, data completion, usage rate and technical practicability of the planned intervention.
2. To analyse the presumed change in care processes before and after the implementation of eIPOS.
3. To explore the acceptability of the ePRO measure for patients and SPHC professionals.

METHODS AND ANALYSIS

Palli-MONITOR is a sequential mixed-methods, two-phase development and feasibility study (figure 1). Each of the two project phases consists of two substudies. The results from substudy I and II will inform an acceptable and validated electronic version of eIPOS which will be used in the feasibility study in phase 2 consisting of substudies III and IV. We follow the MRC guidance and use substudies I and II to develop the intervention (MRC phase 1) and substudies III and IV to test the feasibility of the intervention (MRC phase 2).²²

The project is led by a research team in the Department of Palliative Medicine, University Hospital of the Ludwig Maximilian University (LMU) Munich, supported by two information technology companies. Five SPHC teams participate in Palli-MONITOR based

[figure not shown]

Figure 1 Study design of the project Palli-MONITOR. eIPOS, electronic IPOS; IPOS, Integrated Palliative care Outcome Scale.

on the geographical area: two teams provide care in a mostly urban setting, two teams in a rural area and one team in a mixed region. The project is conducted between 2018 and 2021/2022. Substudies III and IV will continue until 2022.

Development of the intervention (MRC phase 1)

Phase 1 consists of two substudies: for the development of eIPOS, exploring the implementation of eIPOS with stakeholders (substudy I); and testing the equivalence of the developed eIPOS and IPOS (substudy II). Both substudies aim to identify and explore in depth the barriers and facilitators of routinely using an ePRO in a severely ill population and best ways of incorporating this information into everyday practice. Within this development phase, processes and outcomes of implementing eIPOS will be modelled according to implementation science regarding PROs.^{23–25}

Substudy I: qualitative interviews and focus groups

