Substudy III aims to introduce the eIPOS into the routine care processes of each participating SPHC service. In addition to the intervention group receiving eIPOS, there will be two control groups: (a) a prospective control group with patients not receiving the eIPOS, and (b) a retrospective (historical) control group consisting of medical record/chart reviews for patients in the services prior to the introduction of eIPOS. The design of this substudy is summarised in figure 2. All patients cared for by one of the participating SPHC teams are eligible for this study. The intervention consists of patients completing eIPOS for a period of 2 weeks, with corresponding care processes (score review by clinical staff, identifying areas of need and targeting interventions for symptom management accordingly). Participants in the control group, who chose not to use the eIPOS or were ineligible, will not complete any self-report PROs. Care processes for this group will consist of usual care provided by the SPHC service. The retrospective control groups will consist of patients who were cared for by SPHC teams during the last 6 months before the implementation of eIPOS.

[figure not shown]

Figure 2 Substudy III—data collection and inclusion criteria of the quasi-experimental study. *Assessed by the clinical team. eIPOS, electronic Integrated Palliative care Outcome Scale; ESAS, Edmonton Symptom Assessment Scale; QoL, Quality of Life; SPHC, specialised palliative home care.

Table 2 Inclusion criteria for substudy III

Intervention group	Prospective control group	Historical control

 ► Currently cared for by one of the participating SPHC teams (including access to emergency services) regardless of the underlying disease ► ≥ 18 years ► Having the capacity to give written consent ► Not too distressed or ill to participate in the study (assessed by the clinical team) ► Sufficiently fluent in German 	
 ► Currently cared for by one of the participating SPHC teams (including access to emergency services) regardless of the underlying disease ► ≥ 18 years ► Not using eIPOS 	
 ► Inclusion/exclusion criteria will be finalised after analysing data from phase 1 ► Currently planned: inclusion of all patients cared for by the participating SPHC teams (including access to emergency services) during the last 6 months before the implementation of eIPOS

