eIPOS, electronic Integrated Palliative care Outcome Scale; SPHC, specialised palliative home care.

Intervention group

At baseline, a study nurse will introduce the patient to eIPOS. After that, the participant will complete eIPOS every 3 days. There will be no obligation to answer each item of the eIPOS. Standardised procedures (for example: frequency of measurement, time point of introduction) will be finalised after phase 1. The information from self-reported eIPOS will be used in routine care processes of the service.

Prospective control

All patients who are cared for by one of the participating SPHC teams, but do not use the eIPOS, will serve as a control group. No additional interventions are planned for this group. However, care processes for this prospective control group might change because of staff being introduced to training around outcome measurement.

Retrospective control

A retrospective chart review will be conducted to provide information on care processes in the services before the introduction of a self-report PRO measure.

Inclusion criteria

The inclusion criteria are similar to substudy I and summarised in [table 2](#).

Recruitment

Intervention group: patients will be recruited from each participating team with the support from a study nurse. A study nurse will inform eligible patients in detail about the aims, study procedure and requirements. If the patient is interested, the study nurse will make an appointment for the introduction of the electronic system and perform the baseline assessment. The patient will need to give written consent before participation.

Outcome measures

Recruitment as well as drop-out rates, technical feasibility (completeness of each eIPOS) and the influence of eIPOS on provided care will be measured as the primary outcomes of interest.

Secondary outcomes will include change in palliative concerns, quality of life and symptom burden measured

with the eIPOS, the EORTC QLQ-C15-PAL (measuring health-related quality of life of palliative patients with cancer)³⁵ and the Edmonton Symptom Assessment Scale (assessing symptoms of palliative care patients)³⁶ at baseline and after 2 weeks.

Data extracted from medical records for both the intervention and control groups will include the number and severity of palliative symptoms and concerns and the steps taken by professionals for reducing the symptoms. Additionally, the number of unplanned hospital admissions will be collected.

Sample size calculation

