As sample size calculation in feasibility studies should not be based on the primary outcomes of interest,³⁷ the intraindividual comparison of quality of life between baseline and 2-week assessment was used as the basis for the estimation. An assumed small effect of $d=0.20$ (with a minimal clinical difference of 4–9 for the EORTC QLQ scale), power=80% and $\alpha=0.05$ for a Wilcoxon test with paired data lead to a sample size of 164. Based on an assumed drop-out rate of 30%, it is aimed to include 213 participants.

For a better understanding of the feasibility of the sample size, and the possible success of the recruitment plan, the total number of patients cared for by the participating SPHC teams (~1.275 patients/year) will be extracted as well. The control groups will include all patients cared for in the time period explained above.

Data analysis

Quantitative analysis will include descriptive analysis of the user rate of eIPOS, recruitment and drop-out rate as well as analysis of the technical feasibility based on completeness of eIPOS and number of missing values. Intraindividual changes in the secondary outcomes before and after the implementation of eIPOS will be explored using non-parametric tests (either Wilcoxon or Friedman). Number of symptoms and amount of provided care before and after the implementation of eIPOS will be compared using McNemar tests and Cochran tests for changes in proportions.

Substudy IV: acceptability of eIPOS (feasibility)

The methods and procedures will be identical with substudy I. In short, semistructured interviews with patients and focus groups with SPHC professionals will be conducted, focusing on the experience with eIPOS and the influence of it on the received/provided care.

Inclusion criteria

Participants who used the eIPOS in substudy III are eligible for the interviews. Apart from that, inclusion criteria are identical with the inclusion criteria of substudy I. Additional inclusion and exclusion criteria may be defined after analysing data of substudy I.

Recruitment

Recruiting participants for this part will be identical with the approach in substudy I.

Sample size

The same approach for the number of included participants will be followed as in substudy I.

Data analysis

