In this study, the research team will work with a variety of stakeholders to consider different requirements, perspectives and opinions in this very challenging research setting. A mixed-methods approach was chosen to explore different barriers and facilitators of the planned intervention.

Recruitment is a natural challenge in the palliative care setting. Even more so, patients eligible for SPHC suffer from life-limiting diseases with a complex symptom burden. Developing a rapid process for the identification and inclusion of eligible patients with the participating SPHC teams as well as the fact that all study appointments will take place in the patients' home should increase the recruitment rates for all study parts. A limitation of the study is its convenience sample based on staff identification of eligible patients in participating study sites. Therefore, gatekeeping and sampling of only comparatively fitter patients cannot be ruled out completely. We hope to mitigate this sampling bias by training staff and co-designing the intervention with staff from the participating sites. We will compare the sociodemographic details of recruited patients with population data from the services to quantify this possible bias.

The use in clinical practice will depend on the compliance with the newly developed intervention.⁴⁰ Other researchers, for instance, Lang *et al*⁴¹ explored non-compliance with a telemedical intervention for multimorbid patients over 65 years and discovered that missing additional benefits of the intervention, missing content variety and no interest in telemedical care were the main reasons for drop-outs and/or not using the intervention at all. Studies with patients suffering from heart failure or chronic obstructive pulmonary disease testing telemedical interventions have a drop-out rate of around 20% and almost one-third of the patients refuse to participate.⁴²

Therefore, the involvement of patients and professionals is crucial in the development and implementation of eIPOS. In phase 1, barriers and facilitators of the planned intervention will be explored. The results will inform the development of the implementation process. There will also be training sessions on site for each SPHC team between phase 1 and 2 to present results, and to discuss positive as well as negative comments received in phase 1.

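### Substudy III: the care comparison has no stated team stratum, so if uptake and care both differ between the five teams, team mix could be read as an effect of eIPOS

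*Protocol*

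**What the plan says.** The Methods and analysis section describes five participating teams: "two teams provide care in a mostly urban setting, two teams in a rural area and one team in a mixed region".

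Users come from all of them. Under Recruitment in substudy III, "patients will be recruited from each participating team with the support from a study nurse"; no target or quota per team is given. The later Strengths and limitations section adds: "A limitation of the study is its convenience sample based on staff identification of eligible patients in participating study sites".

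The controls are defined differently. The Sample size calculation of substudy III states: "The control groups will include all patients cared for in the time period explained above". The historical group is currently planned as "patients who were cared for by SPHC teams during the last 6 months before the implementation of eIPOS", and Table 2 marks its criteria as still to be finalised. The prospective group is everyone under the teams' care who does not use eIPOS.

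Under Outcome measures, the influence of eIPOS on care is listed among the primary outcomes, and chart data are extracted for the intervention and control groups alike. Under Data analysis, the number of symptoms and the amount of care before and after introduction "will be compared using McNemar tests and Cochran tests for changes in proportions". No team term, stratum or matching is mentioned.

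**The concern.** The user group and the control groups weight the teams by different rules. In the controls each team counts in proportion to its caseload. Among the users each team counts in proportion to how many patients its staff identify and how many agree, and nothing in the design ties that to caseload. The prospective control is the complement of the users, so a team that recruits well is over-represented on one side and depleted on the other.

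If a team that delivers or charts more care also recruits more users, users will seem to receive more care although eIPOS does nothing. If it recruits fewer, a real effect can be hidden. The one planned check on selection compares sociodemographic details with the service populations, which does not touch differences in care or charting between teams.

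**Working it through.** **Plan's own figures.** The protocol gives no effect size or power for the care comparison. The target of 213 users reproduces as 164 × 1.3 = 213.2, but 164 rests on the paired change in quality of life and says nothing about this comparison. It is used below only as the number of users.

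**Inputs from the protocol.** Five teams; 213 users; about 1,275 patients a year ("the total number of patients cared for by the participating SPHC teams (~1.275 patients/year) will be extracted as well", with the point read as a thousands separator). Six months of caseload gives 1,275 / 2 ≈ 637 historical controls.

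**Assumptions, since the protocol gives none.** Equal caseloads (20% per team); each team's share of users; each team's rate of a documented care item; no true effect of eIPOS; one year for the prospective group, giving 1,275 − 213 = 1,062 non-users; and an independent two-group test of proportions at two-sided 5%, because the groups are different patients.

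**Formula.** With user shares u_k, control shares c_k and team rates p_k, the false gap is Σ (u_k − c_k) p_k. It is 0 if u_k = c_k for every team, or if all p_k are equal.

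**Extreme aligned case, historical controls.** Shares 40/30/15/10/5%, rates 70/60/50/40/30%:
- Users: 0.70×0.40 + 0.60×0.30 + 0.50×0.15 + 0.40×0.10 + 0.30×0.05 = 0.59; controls 0.50; gap 9 points.
- SE = √(0.59×0.41/213 + 0.25/637) = 0.039; z = 0.09/0.039 = 2.3; rejection probability about 63%.

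**Milder variants, same method.**
- Same shares, rates 60/55/50/45/40%: 0.545 against 0.50, gap 4.5 points, about 21%.
- Shares 30/25/20/15/10%: gap 2.5 points (about 10%) with rates of 60 to 40%, and 5 points (about 25%) with rates of 70 to 30%.

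**Separate simulation with other assumed shares** (4,000 runs per scenario, no true effect):

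| User shares by team (%) | Team rates (%) | Gap v 637 historical | Rejects | Gap v 1,062 non-users | Rejects |
|---|---|---|---|---|---|
| 20/20/20/20/20 | 70–30 | 0 | 5% | 0 | 6% |
| 28/24/20/16/12 | 60–40 | 2.0 points | 8% | 2.4 points | 9% |
| 28/24/20/16/12 | 70–30 | 4.0 points | 18% | 4.8 points | 25% |
| 40/25/15/12/8 | 60–40 | 3.9 points | 16% | 4.6 points | 24% |
| 40/25/15/12/8 | 70–30 | 7.7 points | 50% | 9.2 points | 71% |

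A team-stratified Mantel-Haenszel test on the same simulated data rejected in about 4 to 6% of runs in every scenario. Against the non-users the gap is wider for the same shares, because strong recruiters are depleted there.

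**The case against.** **Uneven uptake is not documented.** A reader might infer that users are drawn unevenly. The protocol says only that they come from each team. The bias needs uneven uptake, differing care rates and an association between the two, and all three are assumed here. This stands: the point is conditional. What remains is that nothing in the design secures even uptake in a sample that depends on staff at each site.

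**The contrast is not spelled out.** The Data analysis section speaks of before and after introduction. If the whole caseloads of the same five teams were compared across the two periods, team mix would be roughly balanced. The comparison of users with controls is inferred from the two control groups and from the chart data taken for all groups. It is the more natural reading, since a whole-caseload comparison would leave the separate prospective control without a role, but the text does not fix it.

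**The rejection rates belong to a test that the protocol does not name.** McNemar and Cochran's Q need matched observations. In a comparison within patients, team would cancel. Between different patients those tests do not fit, which is a separate problem. A stratified Cochran-type test is not excluded by the wording either.

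**Centre adjustment may be in an analysis plan that is not shown.** This is a partial answer, because the protocol does name its tests here and gives them no stratum.

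**A larger bias is left.** Controls include patients who declined or were ineligible, and a team term does not remove that. This also stands.

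**Conclusion.** The point holds in conditional form. The protocol sets a convenience sample from five differing teams against full-caseload controls and names tests with no stated team stratum for an outcome that it lists as primary. If uptake and care both differ between teams, a comparison of users with controls would confound team with eIPOS use.

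The size cannot be derived from the protocol. The 63% and 71% figures come from scenarios in which recruitment and care rates fall together across the teams; a reader might take them as the expected error rate, and nothing in the protocol supports that. The moderate scenarios, at 8 to 25%, are no less assumed.

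Nor does the point invalidate the study, as a reader might also infer. It is described as exploratory, its sample size is deliberately not based on the primary outcomes, and a cluster-randomised trial is to follow. The consequence is a misleading signal for that trial, not a wrong confirmatory conclusion. The change is worth making because it is nearly free.

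**What to change.** In the Data analysis section of substudy III:

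1. State which groups are contrasted for symptoms, care and unplanned admissions: users with historical controls, users with concurrent non-users, or whole caseloads across periods.
2. Require a team code in the chart extraction. Data management says that records are extracted anonymously and does not say whether the team is kept.
3. Make these comparisons within team: a regression with team as a fixed factor, or a team-stratified Mantel-Haenszel estimate for yes/no items.
4. List the five team-specific results, with recruitment by team, beside the combined estimate. This is also useful for designing the cluster-randomised trial.
5. Say that this removes differences in team mix only, and that selection of patients into eIPOS use remains.

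The cost is a few lines of text, one variable in the extraction and four degrees of freedom (five teams minus one). No extra patients are needed.

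### If the before-and-after comparison of symptoms and care sets eIPOS users against the historical chart cohort, McNemar and Cochran's Q do not fit, because the patients differ and are not matched.

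*Protocol*

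**What the plan says.** The Data analysis paragraph of substudy III (Protocol) plans the comparison of symptom counts and provided care in one sentence, which ends: "amount of provided care before and after the implementation of eIPOS will be compared using McNemar tests and Cochran tests for changes in proportions". It does not say which groups supply the before and the after data.

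Other parts of the protocol bear on this:

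- **Phase 2 objectives (Introduction).** Objective 2 is "To analyse the presumed change in care processes before and after the implementation of eIPOS".
- **Substudy III, opening paragraph.** The retrospective control group consists of "patients who were cared for by SPHC teams during the last 6 months before the implementation of eIPOS".
- **Table 2, historical control.** Criteria are to be finalised after phase 1. "Currently planned: inclusion of all patients cared for by the participating SPHC teams" in that 6-month period.
- **Section on the retrospective control.** Its purpose is given in these words: "chart review will be conducted to provide information on care processes in the services before the introduction of a self-report PRO measure".
- **Outcome measures, chart data.** "Data extracted from medical records for both the intervention and control groups will include the number and severity of palliative symptoms and concerns", together with the steps professionals took to reduce symptoms.
- **Outcome measures, primary outcomes.** Recruitment and drop-out rates, completeness and "the influence of eIPOS on provided care will be measured as the primary outcomes of interest". The Abstract names only recruitment rates and completeness of eIPOS as primary.
- **Data analysis, the sentence before.** "Intraindividual changes in the secondary outcomes before and after the implementation of eIPOS will be explored using non-parametric tests". The tests named there are Wilcoxon and Friedman.

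**The concern.** McNemar's test works on the discordant cells of a paired two-by-two table. Cochran's Q extends it to three or more related binary observations. Both need the same patient, or an individually matched one, in each condition.

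The text describes one source of information on care processes before eIPOS: charts of patients treated earlier. The eIPOS users are consenting patients in current care. Apart from a few long-stay patients who might fall in both periods, these are different people in unequal numbers, and no matching is described. If they are the two sides of the comparison, the named tests cannot be applied as they stand. An analyst would either have to pair unrelated patients, so that the result depends on who is paired with whom and most historical charts go unused, or depart from the written plan.

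The comparison serves phase 2 objective 2 and an outcome that the Outcome measures section, though not the Abstract, lists as primary. The results are meant to inform a later cluster-randomised trial.

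**Working it through.** The protocol gives no figure for this comparison, so there is none to reproduce. The check has two parts.

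**1. Which patients are compared?**

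For different patients:
- The opening paragraph of substudy III uses almost the same before-implementation phrase to define the historical group by calendar time.
- The Retrospective control section gives that chart review the purpose of describing earlier care processes.
- The Outcome measures section has symptoms and steps taken, the measures in the disputed sentence, extracted for intervention and control groups alike.
- Objective 2 speaks of care processes, not of change within a patient.

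For the same patients:
- The preceding sentence uses the same before-and-after phrase for intraindividual change.
- All four tests named in the paragraph can be read as related-sample tests.

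The first reading has more support. The second is not excluded.

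**2. What would pairing unrelated patients cost?** (illustration only)

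Inputs:
- about 1,275 patients a year, from the sample size section of substudy III
- 6 months of charts under even flow (assumption): 1,275 × 0.5 = 637.5, about 638
- 213 users planned; after the stated 30% drop-out, 213 × 0.7 = 149.1, about 149
- a proportion near 0.5 (assumption), so p(1 − p) = 0.25

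Formulas for the 95% half-width of the difference in proportions:
- all charts, independent groups: 1.96 × √[0.25 × (1/n + 1/637.5)]
- n arbitrary one-to-one pairs of unrelated patients: 1.96 × √[0.25 × 2/n]

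| Users n | All charts | Arbitrary pairs | Variance ratio |
|---|---|---|---|
| 213 | 1.96 × √(0.25 × 0.006263) = 7.76 points | 1.96 × √(0.25 × 0.009390) = 9.50 points | 0.009390 / 0.006263 = 1.50 |
| 149 | 1.96 × √(0.25 × 0.008280) = 8.92 points | 1.96 × √(0.25 × 0.013423) = 11.35 points | 0.013423 / 0.008280 = 1.62 |

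With patient flow 20% lower or higher (510 or 765 charts) and 213 users, the variance ratio is 1.41 or 1.56. Halving the annual number may undercount patients whose care spans both half-years; a larger cohort would raise the ratio.

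Dependence on the pairing: take one fixed data set with 128 of 213 users and 318 of 637 historical patients positive (about 60% and 50%, assumed rates). The independent chi-square test gives p = 0.010. Over 5,000 random pairings of the same data, the McNemar p-value has a central 95% range of about 0.001 to 0.33.

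Type I error: in 20,000 simulated trials with both proportions at 0.50, 213 users and 638 charts, McNemar on random pairs rejects in 4.9% and the chi-square test on all charts in 5.0%. Size is not inflated.

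**The case against.** The strongest reply is that the paragraph means a within-patient analysis throughout. Two consecutive sentences share the before-and-after phrase. In the first it must refer to the individual patient, because the secondary outcomes are measured at baseline and after 2 weeks. Wilcoxon with Friedman, then McNemar with Cochran, form two parallel sets of related-sample tests, and eIPOS is completed every 3 days. On that reading the tests suit binary items, and the chart review may be purely descriptive. This stands as a real possibility. Against it, the disputed sentence lacks the word intraindividual and concerns measures that are extracted for the control groups too.

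A reader might add that the text defines no chart window before eIPOS within a patient, and take this as proof of the historical reading. That does not follow. Figure 2, which covers data collection, was not available in the text examined, and such windows may be left to a statistical analysis plan.

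It can also be said that nobody plans one-to-one pairing. That is correct: no section proposes it. The widths above show what a literal use of the named tests would cost. They do not predict what the analysts would do.

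Finally, the study is exploratory, the two lists of primary outcomes differ, and no decision rule hangs on this comparison. These facts limit its importance but do not make a related-sample test suitable for unrelated patients.

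**Conclusion.** The point holds conditionally. If number of symptoms and amount of care are compared between eIPOS users and the historical chart patients, which several sections support, McNemar and Cochran's Q do not fit. The same applies to a comparison with the prospective controls, who are also different patients. If only repeated measures in the same users are meant, the tests are acceptable for binary items.

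The size is illustrative: variance about 1.5 times as large with 213 users and 1.6 times with 149, given even patient flow, a proportion near 50%, historical criteria as currently planned, and a pairing that the protocol does not propose. The harm would be an arbitrary result and unused charts.

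Two stronger conclusions might be inferred, and the protocol supports neither. One is that it definitely applies paired tests to independent groups; the sentence is too open for that. The other is that false-positive findings would increase; the simulated size stays near 5%.

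The Cochran test is read here as Cochran's Q because it stands beside McNemar for changes in proportions. If another Cochran test is meant, McNemar would still not fit different patients. The sentence should be corrected, with medium confidence that the historical comparison is the one intended.

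**What to change.** In the Data analysis paragraph of substudy III:

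- State which groups and periods the comparison of symptoms and provided care uses.
- State that comparisons of eIPOS users with historical or prospective control patients use independent-group methods, for example a chi-square test for binary items and a rank test for numbers of symptoms or care steps.
- Restrict McNemar and Cochran's Q to repeated binary measures in the same patient.
- If only a within-patient comparison is meant, say so, and say how the historical cohort is used.

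Adjustment for team and case mix is optional and not needed to resolve this point. The cost is a wording change and slightly more analysis work. No extra patients or chart items are needed.
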